1 BACKGROUND INFORMATION

1.1 Tenalisib (RP6530)

The phosphoinositide-3-kinases (PI3Ks) are a family of enzymes involved in various cellular functions, including cell proliferation and survival, cell differentiation, intracellular trafficking and immunity.^[1-3] Tenalisib is a highly specific and orally available dual PI3K δ/γ inhibitor with nano-molar inhibitory potency and several fold selectivity over α and β PI3K isoforms. The specificity of Tenalisib towards PI3K δ and γ is evidenced by >1000 and >100-fold selectivity over α and β isoforms in an enzyme-based assay. Chemically, Tenalisib is an iso-flavone substituted adenine.

1.1.1 Summary of Pre-Clinical Evaluation

Tenalisib has equimolar potency against both PI3K δ/γ isoforms in enzyme, cell, and blood-based assays. Additionally, the compound inhibited antigen-induced superoxide or cytokine release from primary human neutrophils or monocytes at nano-molar concentration indicating a potential in modulation of the tumor microenvironment. Studies using immortalized B and T lymphoma cell lines demonstrated the anti-proliferative effect of Tenalisib coupled with induction of apoptosis and a concomitant inhibition of the downstream biomarker, pAKT. Similarly, cytokine induced pAKT was inhibited in malignant primary CTCL cells isolated from patient donors. Tenalisib induced apoptosis of patient derived primary CTCL cells following 48 hr incubation.

In vivo efficacy of Tenalisib was confirmed in a subcutaneous mouse MOLT-4 xenograft model representative of human T-cell acute lymphoblastic leukemia. Oral administration of 50 mg/kg/BID over an 18-day period resulted in a significant delay in tumor growth.^[4] In 28-days toxicity studies in rat and dog, once daily oral administration of Tenalisib was well tolerated. Target organ effects were observed in thyroid and liver. The no-observed-adverse-effect level (NOAEL) was 20 mg/kg/day in rat and 10 mg/kg/day in dog.

Refer to the Investigator's Brochure (IB) for detailed background information on Tenalisib.^[5]

1.1.2 Summary of Clinical Evaluation

To date, Tenalisib has been evaluated in four clinical trials:

1. A Phase I Dose Escalation Study Evaluating the Safety and Efficacy of RP6530, a dual PI3K δ/γ inhibitor, in Patients with Relapsed or Refractory Hematologic Malignancies (European study: Protocol Number RP6530-1301) Status: Completed
2. A Phase I/Ib, Dose Escalation Study to Evaluate Safety and Efficacy of RP6530, a dual PI3K δ/γ inhibitor, in Patients with Relapsed or Refractory T-cell Lymphoma (US study: Protocol number RP6530-1401). Status: Recruitment completed. Study Ongoing
3. An open label, randomized, single dose, crossover study to evaluate food effects on relative bioavailability of RP6530 administered in fasting and fed conditions in healthy volunteers (Food effect study, Protocol no: RP6530-1501). Status: Completed
4. An Open label, Phase I/II study to evaluate the safety and efficacy of RP6530, a novel PI3K δ/γ dual inhibitor given in combination with an anti-PD-1 therapy, Pembrolizumab in adult patients with relapsed or refractory Classical Hodgkin's lymphoma (cHL). Status: Ongoing and currently recruiting.

- **Safety:**

In RP6530-1401 study, a total of 58 patients were treated at 200 mg BID (n=4), 400 mg BID (n=4), 800 mg BID (Fasting) (n=44) and 800 mg BID (Fed) (n=6) in both dose escalation and dose expansion cohorts. Tenalisib demonstrated acceptable safety and tolerability profile up to 800 mg BID (fasting). Tenalisib 800 mg BID (Fasting) was considered as MTD dose in patients with T-cell lymphoma. Majority of AEs include transaminitis, skin rash. Treatment related Grade ≥ 3 includes AST/ALT elevation (n=12), rash (n=4), hypophosphatemia (n=2), neutropenia (n=1), INR Increase (n=1), sepsis (n=1), pyrexia (n=1), diplopia secondary to neuropathy (n=1), drug reaction (n=1), and bacteremia (n=1). Treatment related SAE reported were pyrexia (n=1), raised INR (n=1), sepsis (n=1), diplopia secondary to neuropathy (n=1), drug reaction (n=1) and bacteremia (n=1).

- **Pharmacokinetics:**

In RP6530-1401 study, at the 200 mg dose, AUC_{0-t} and C_{max} were 3713.94 h*ng/mL and 1463.57 ng/mL at C1D1 respectively; corresponding levels at C2D1 were 3985.52 h*ng/mL and 1781.24 ng/mL. Similarly, at the 800 mg dose (fed), AUC_{0-t} and C_{max} were 13204.17 h*ng/mL and 2988.66 ng/mL at C1D1 respectively; corresponding levels at C2D1 were 12737.21 h*ng/mL and 3234.50 ng/mL. At the 800 mg dose (fasting), AUC_{0-t} and C_{max} were 14033.67 h*ng/mL and 4174.71 ng/mL at C1D1 respectively; corresponding levels at C2D1 were 13210.24 h*ng/mL and 3395.28 ng/mL. Based on C_{max} and AUC, dose proportionality was observed up to the 800 mg dose. Upon increasing doses, no changes in T_{max} were observed and while changes in $T_{1/2}$ were observed, steady state PK parameters of Tenalisib as determined on C2D1 revealed no accumulation.

- **Efficacy:**

In RP6530-1401 study, response assessments of the thirty-five evaluable patients receiving at least two cycles of Tenalisib showed an ORR of 46% (16/35 patients) out of which 3 (9%) were CR and 13 (37%) were PR. Eleven patients showed stable disease (31%). Indication specific analysis showed an ORR of 47% (7/15, 3 CR, 4 PR) in PTCL and 45% (9/20, 9 PR) in CTCL. Effect of RP6530 on associated correlative markers in PTCL (sIL-2R and CD30) and CTCL (IL-31, IL-32 α , and CTACK) patients that were either a CR, PR, or SD on C3D1 showed decreased plasma concentrations of markers with the reductions being most pronounced for CD30 (57%) and IL-31 (33%) in the respective patient populations.^[6]

1.2 Romidepsin

Romidepsin is a histone deacetylases (HDAC) inhibitor and was approved by FDA for the treatment of CTCL and PTCL in 2009 and 2011 respectively for the patients who have received at least one prior systemic therapy. A pivotal phase II study on Romidepsin in 131 patients with relapsed or refractory PTCL showed an ORR of 26 % (CR rate of 15 %), progression free survival (PFS): 4 months and DoR of 13 months.^[7] Similarly, Romidepsin was evaluated in 2 multicenter, single-arm clinical studies in patients with CTCL. Cumulative, response rate (ORR) in 167 patients was 35 % (CR rate of 6%) and DoR of 13 months.^[7]

1.3 Study Rationale

1.3.1 Rationale for Study Population

T-cell lymphomas (TCL) comprise a heterogeneous group of lymphoid malignancies arising from mature T-cells. Peripheral T cell lymphoma (PTCL) constitute 10–12 % of non-Hodgkin's lymphomas (NHL) in Western countries but are relatively common in Eastern Asian, constituting about 20 % of mature NHL.^[8] There is no consensus regarding optimal treatment for PTCL, especially in relapsed or refractory cases, which have very poor prognosis. High-dose chemotherapy followed by autologous stem cell transplantation (ASCT) has been accepted as a salvage treatment for eligible patients, although the evidence is unclear.^[9] Moreover, the overall prognosis remains dismal in patients unsuitable for ASCT.

Cutaneous T-cell lymphomas (CTCLs) represent a group of rare, clinically and pathologically heterogeneous diseases. The incidence of CTCL has been increasing and is currently 6.4 per million persons, with the highest incidence rates being reported among males and African-Americans. Mycosis fungoides (MF) is the most common primary CTCL variant and is closely related to a rare leukemic variant, Sézary syndrome (SS). Skin-directed therapies, such as psoraleen plus ultraviolet A in combination with retinoids or interferon, are used in the early stage disease and generally produce good, long-term responses. Patients with advanced-stage disease require a multidisciplinary approach that includes combinations of skin-directed therapies, biologic-response modifiers and systemic chemotherapeutic agents. Although patients with early stages of disease have an excellent prognosis, ~25% develop progressive disease.^[10-12] The prognosis for patients presenting with advanced-stage disease is poor.^[10, 11, 13, 14]

Over recent years, several single-agent therapies have proven to be effective in relapsed/refractory PTCL. Pralatrexate, romidepsin, and belinostat are all approved broadly for PTCL with ORR's in phase II studies of 29, 25, and 26 %, respectively. Brentuximab vedotin is also approved in relapsed ALCL with an ORR of 86 % in a small phase II trial.

Despite recent progress, there are hurdles to overcome in managing patients with PTCL as responses with these therapies are not optimal (all approved therapies except brentuximab has response rate <30%). Given the aggressive nature of PTCL, which has a poor prognosis, this patient population represents an unmet medical need.

CTCL patients are responsive to treatment in the early stages; patients have a long duration of survival but are rarely cured of the disease. For refractory early-stage and advanced-stage disease (IIB-IV), a multidisciplinary approach is used that include bexarotene, interferon α , extracorporeal photopheresis, histone deacetylase inhibitors (vorinostat and romidepsin), and antibody therapies such as alemtuzumab, systemic chemotherapy, and allogeneic transplantation. Though, these agents, alone or in combinations, are associated with high response rates, unfortunately response is often of limited duration (frequently measured in months) and especially in advanced cases, characterized by frequent recurrences, probably due to treatment resistance. Therefore, the prognosis for patients presenting with advanced-stage disease generally poor^[10, 11, 13, 14]. Hence, novel therapeutic agents, either alone or in combination, are needed to achieve better disease control in these patients.

1.3.2 Rationale for Combination of Tenalisib and Romidepsin

Modification of histones by acetylation plays a key role in epigenetic regulation of gene expression and is controlled by the balance between histone deacetylases (HDAC) and histone acetyltransferases (HAT). HDAC inhibitors induce cancer cell cycle arrest, differentiation and cell death, reduce angiogenesis and modulate immune response.

Recently it is recognized that TCL may be a disease characterized by epigenetic dysregulation, partly explained by TCL sensitivity to histone deacetylase (HDAC) inhibitors. Early phase clinical studies have demonstrated that combination therapy with epigenetic therapies such as HDAC inhibitors plus other agents known to have activity in T cell lymphoma have enhanced clinical benefit for this group of diseases. Therefore, HDAC inhibitors have been increasingly used as a platform to which other novel therapies or chemotherapy can be added.

Pre-clinical experiments demonstrated the synergistic anti-tumor activity achieved by combining PI3K inhibitor with HDAC inhibitor in B-cell lymphoma cell lines and primary NHL/ CLL cells. These experiments indicated that interference with PI3K signalling dramatically increases HDAC inhibitor-mediated apoptosis in malignant haematopoietic cells - this might be through either AKT-dependent or AKT-independent mechanisms. Moreover, the dramatic increase in HDAC inhibitor-related apoptosis observed in PI3K inhibitor-treated cells appears to be related to the disruption of the ERK signalling pathway.^[15]

Synergistic potential of the combination of Tenalisib and Romidepsin in attenuating T-cell lymphoma cell proliferation was determined using HuT-78, HuT-102, MOLT-4, and Jurkat. Cells were incubated with desired concentrations of DMSO (Vehicle), Tenalisib (RP6530), or a combination of Tenalisib (RP6530) and Romidepsin for 72 hours cell viability estimated in the MTT-based assay. Combination effect was determined by calculating the Bliss score where *scores >10* indicate synergism. Among the cell lines evaluated, synergism between RP6530 and Romidepsin was most evident in the CTCL cell lines, Hut-78 and HuT-102.

Figure 1. Inhibition of Cell Growth in T-Cell Lymphoma Cell Lines

A. HuT-78

Excess over Bliss Score		RP6530 (nM)					
	Conc (nM)	0	500	1000	3000	5000	10000
Romidepsin (nM)	0						
	3		4.60	1.57	16.83	8.64	14.28
	4		10.37	2.63	27.00	28.29	33.47
	5		13.50	15.53	30.11	12.29	29.05
	6		-1.95	12.46	10.93	27.21	36.13
	8		7.61	23.33	22.34	23.91	32.42

B. Hut-102

Excess over Bliss Score		RP6530 (nM)					
	Conc (nM)	0	500	1000	3000	5000	10000
Romidepsin (nM)	0						
	3		-2.08	14.34	0.39	6.95	20.15
	4		2.55	12.95	9.15	8.35	26.22
	5		-13.32	-6.69	-7.72	-2.29	25.95
	6		-8.39	-7.28	-1.32	2.90	11.33
	8		-13.51	-6.08	-12.95	-9.42	11.03

In the clinical setting, individually, both Tenalisib and Romidepsin has shown good response rate of > 25 % (ORR) and durable response for >4 months in TCL patients in relapsed/refractory setting. It is therefore hypothesized that a Tenalisib/Romidepsin combination has the potential to synergize and improve depth and durability of responses in these patients.

1.3.3 Rationale for Dose Selection

The safety and tolerability of Tenalisib has been established at 800 mg BID in an ongoing study in patients with relapsed/refractory T-cell lymphoma. Given the fact that both Romidepsin and Tenalisib have non-overlapping toxicity profiles, half of the optimal dose of Tenalisib (400 mg BID) and one dose below the approved dose of Romidepsin (12 mg/m²) are considered reasonable as starting doses of the combination from safety point of view. In line with the approved prescribing information, Romidepsin will be administered at Day 1, 8 and 15 in a 28-day cycle. The lower doses may be selected on the basis of emerging toxicities of each of the agents given the distinctive nature of toxicities.

1.4 Benefit and Risk

It is expected that proposed combination of Tenalisib with Romidepsin has the potential to improve response rates and increase the durability of response. However, all the patients in clinical trials generally cannot expect to receive direct benefit from treatment during participation, as clinical trials are designed to provide information about the safety and effectiveness of an investigational medicine. Additional details regarding specific benefits and risks for subjects participating in this clinical trial may be found in the accompanying IB and Informed Consent documents.

2 TRIAL OBJECTIVES

2.1 Primary Objectives

- To characterize safety, tolerability and to establish the maximum tolerated dose (MTD) of Tenalisib in combination with Romidepsin in patients with R/R T-cell lymphoma.

2.2 Secondary Objectives

- To assess the preliminary anti-tumor activity of various dose levels of Tenalisib in combination with Romidepsin as determined by the Objective Response Rate (ORR) and Duration of Response (DoR).
- To characterize the Pharmacokinetics (PK) of Tenalisib and Romidepsin when given in combination.

2.3 Exploratory Objectives

- To correlate clinical efficacy with markers that include but are not limited to quantitative and qualitative measurements of malignant cells, cytokines, and chemokines in blood/serum.

3 TRIAL DESIGN

3.1 Trial End Points

3.1.1 Primary Endpoint

- **Safety:**
Adverse Event (AE), Grade 3/ 4 AEs, Serious and fatal Adverse Event (SAE), graded using NCI CTCAE Version 5.0.

3.1.2 Secondary Endpoints

- **Efficacy:**

1. **Objective Response Rate (ORR)**, defined as sum of CR and PR rates, assessed according to the Lugano Classification for initial evaluation, staging, and response assessment of Hodgkin/non-Hodgkin lymphoma in PTCL patients; and according to the modified Severity Weighted Assessment Tool (mSWAT) in CTCL patients.
2. **Duration of Response (DoR)**, calculated as time from the initial response to documented disease progression.

- **Pharmacokinetics:**

PK Parameters [AUC $(0-\infty)$, AUC $(0- t)$, C_{max} , t_{max} , K_{el} , and $t_{1/2}$] of Tenalisib and Romidepsin.

3.1.3 Correlative/Exploratory End Points

Correlative markers include baseline and on-treatment serum levels of chemokines, cytokines, antibodies to tumor antigens, and other immune mediators (e.g. sIL2R and CTACK for PTCL; CD30, IL-31 and IL-32 for CTCL) as deemed relevant by the sponsor.

3.2 Design of Trial

This is a multi-center, open label, non-randomized, two-part Phase I/II study of Tenalisib in

combination with Romidepsin in adult patients with relapsed/refractory TCL. The first part is an open-label, 3+3 dose escalation, Phase I study for MTD determination. The second part is a Phase II, dose expansion to delineate the safety and anti-tumor activity of the combination at the MTD/optimal dose.

In dose escalation, a minimum of 2 and maximum 18 patients will be enrolled in three dose levels unless additional dose levels are required to reach MTD/ optimal dose. In dose expansion, up to 24 TCL patients will be enrolled (Group 1= 12 PTCL patients and Group 2= 12 CTCL patients).

The study will end when all ongoing subjects have reached their third tumor assessment on Cycle 8/Day 1 (C8D1) or have discontinued from the study for any reason, whichever is earlier. At the end of the study, all ongoing patients with no evident disease progression will be given the opportunity to enroll in an open-label compassionate use study protocol and will be followed up.

3.2.1 Phase I: Dose Escalation

3.2.1.1 Dose Escalation Cohorts

Sequential dose escalation will begin with Cohort 1. A minimum of three patients will be enrolled at each dose level. Dose levels will be increased in successive increments according to the dose escalation cohorts mentioned in Table 1. Escalation to the next cohort will occur if no patient within a three-patient cohort or one in six patients experiences a dose limiting toxicity (DLT). De-escalation to different lower doses in case of DLT criteria met will be done as per the discretion of the Safety Review Committee (SRC). The highest doses of the combination (Tenalisib at 800 mg BID plus Romidepsin IV 14 mg/m²) will be considered as optimal in case there is no DLT at this dose level.

Table 1: Dose Escalation Scheme

Cohort	N	Tenalisib ¹	Romidepsin ²
Cohort 1	3-6	Tab. 400 mg PO twice a day	IV 12 mg/m ² on Day 1, 8 and 15
Cohort 2	3-6	Tab. 600 mg PO twice a day	IV 12 mg/m ² on Day 1, 8 and 15
Cohort 3	3-6	Tab. 800 mg PO twice a day	IV 14 mg/m ² on Day 1, 8 and 15

Note: Alternate dose levels/dosing schedules may be considered by the SRC if deemed essential based on emerging safety and PK data.

¹*In case the dose (e.g. 800 mg BID) is leading to DLT of the combination, the dose of Tenalisib will be reduced to lower dose (e.g. 600 mg BID) and will be evaluated for safety in a separate cohort.*

²*In case the dose (e.g. 14 mg/m²) is leading to DLT of the combination, the dose of Romidepsin will be reduced to lower dose (e.g. 12 mg/m²) and if required further to 10 mg/m² and will be evaluated for safety in a separate cohort.*

Notes:

- For dose escalation decision, safety data of the first 28-days follow up and PK data of C1D1 and C1D8 is essential.
- The dose escalation may occur if no patient within a three-patient cohort experiences a DLT as defined in Section 7.6 If one of three patients within a 3-patient cohort experiences

a DLT, an additional three patients will be treated at the same dose level. If one of six patients within a dose level experiences a DLT, dose escalation will continue. If two or more of six patients within a dose level experience a DLT, that dose level will be defined as exceeding MTD, no further dose escalation will occur. The previous dose level will be considered the MTD or de-escalation to lower dose level will be done as per the discretion of the Safety Review Committee (SRC). Once the MTD/optimal dose of the combination is established; the same doses will be expanded to further elucidate safety and efficacy. Multiple expansion cohorts will be opened at different dose levels, if deemed necessary.

- If two of the first 3 patients in a cohort experience a DLT, that dose level will be defined as exceeding MTD, no further dose escalation will occur. The previous dose level will be considered the MTD and will be expanded to further elucidate safety and to evaluate efficacy.
- The actual number of dose cohorts explored will depend upon the MTD and the safety profile observed during the conduct of the trial. Intermediate dose levels and dosing schedules may be explored if deemed appropriate.
- An optimal dose of combination is defined as the threshold doses of individual drugs at which Tenalisib/Romidepsin combination shows clinical activity/efficacy (shows complete response or partial response) in the disease population and is at or below the maximum tolerated dose.

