3.2.2 Phase II: Dose Expansion

After establishing the MTD/optimal dose, the Phase II (Dose Expansion) will be opened as approved by the SRC to enroll two groups of patients.

Table 2: Dose Expansion

Group	N	Patient population	Tenalisib	Romidepsin
Group 1	12	R/R PTCL	MTD/Optimal dose	MTD/Optimal dose on Day 1, 8 and 15
Group 2	12	R/R CTCL	MTD/Optimal dose	MTD/Optimal dose on Day 1, 8 and 15

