3.6.3 Stopping Rule for Dose Expansion

After establishing the MTD/optimal dose, the Phase II expansion part will be opened as approved by the SRC. The SRC will continue to monitor safety of the combination (or toxicity trends that may be of concern) at interval of 3 months from initiation of expansion cohort till the completion of the study. Safety/toxicity will be monitored across cohorts combined together. The SRC will have discretion to terminate the trial if there are major safety concerns.

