7.6.3 Determination of Dose-limiting toxicity

The patient population used for determination of MTD will consist of patients who have met the minimum safety evaluation requirements of the study, and/or who have experienced a DLT. The data of at least 3 patients will be required for DLT assessment.

- DLT assessment period will be 28-days (inclusive) (will begin on C1D1 and end on C2D1), unless extended by the medical monitor.
- Patients must have been treated with at least 2 doses of Romidepsin and minimum 14 days with Tenalisib in the first cycle to be considered eligible for safety assessment unless identified to have a DLT.
- *Patients experiencing DLT after initiating combination will be considered evaluable regardless of the number of doses received (Please note Romidepsin alone will be administered on Day 1, therefore patient will not be considered for MTD assessment if patient develops DLT on these days).*

If a patient withdraws from the study during Cycle 1 due to any reason other than DLT (e.g. disease progression or consent withdrawal) and does not meet the minimum requirements for inclusion in the MTD-determining population described above will be replaced.

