7.6.4 Maximum Tolerated Dose (MTD)

The MTD is the highest dose of the combination at which 0 of 3 patients or 1 of 6 patients experience a DLT during 1 cycle (28 days) of therapy. If 2 or more patients in a dosing group experience a DLT, the MTD has been exceeded.

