9.2 Determination of Sample Size

Part 1: In Dose Escalation, three patients per cohort are considered appropriate for the assessment of overall safety and tolerability and for providing adequate confidence for dose escalation. No formal sample size and power analysis is done. Accordingly, total 2-18 patients will be enrolled in 3 escalating cohorts unless additional dose levels are required to reach MTD/ optimal dose. Optimal dose will be determined by the SRC.

Part 2: Total 24 patients with relapsed/refractory TCL will be enrolled in two groups (12 patients in each group). Twelve patients per group is considered appropriate for assessment of preliminary anti-tumor activity of the combination. However, the SRC may modify the sample size due to unforeseen clinical situations.

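### A dose level can be named the MTD, or optimal at Cohort 3, and opened to up to 24 expansion patients on 0 DLTs in 3 patients, because no text requires six DLT-evaluable patients there first

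*Protocol*

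**What the plan says.** Protocol 3.2.1.1 sets the escalation rule. "A minimum of three patients will be enrolled at each dose level", and Table 1 gives 3 to 6 per cohort. Escalation continues after 0 of 3 or 1 of 6 DLTs. The second three patients are added only when one of the first three has a DLT.

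If two of the first three have a DLT, that level exceeds the MTD, and for the level below: "The previous dose level will be considered the MTD and will be expanded to further elucidate safety and to evaluate efficacy". Cohort 3, the top level, "will be considered as optimal in case there is no DLT at this dose level", with no patient number attached.

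Protocol 7.6.4 matches this: "The MTD is the highest dose of the combination at which 0 of 3 patients or 1 of 6 patients experience a DLT". Protocol 7.6.3 adds: "The data of at least 3 patients will be required for DLT assessment". SAP 5.1 repeats the escalation rule, the cohort sizes and the three-patient data requirement.

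Expanded here means Phase II, not filling the cohort to six. The preceding note in 3.2.1.1 expands the dose once the MTD or optimal dose is established, and 3.2.2 says that after this step "the Phase II (Dose Expansion) will be opened as approved by the SRC". Up to 24 patients then enter (Protocol 3.2).

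**The concern.** Establishing the MTD is part of the primary objective, and the level so named is the starting point for treating up to 24 more patients. The reason given for three patients is that "three patients per cohort are considered appropriate for the assessment of overall safety and tolerability and for providing adequate confidence for dose escalation" (Protocol 9.2). That supports a step to the next cohort. It does not address whether three patients are enough to settle the dose for expansion.

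No later rule tests the choice. SAP 10.6.2 summarises DLTs for escalation only. In expansion the Safety Review Committee (SRC) reviews safety every 3 months with cohorts combined (Protocol 3.6.3): "The SRC will have discretion to terminate the trial if there are major safety concerns". No toxicity rate is attached. If the true first-cycle DLT rate at the chosen level were 33% (an assumption), about 24 × 0.33 = 8 of 24 expansion patients would be expected to have an event of DLT type.

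**Working it through.** **Plan's own figures.** 3 cohorts × 6 = 18 and 2 groups × 12 = 24, both as stated. The lower limit of 2 for Phase I does not follow from three per level; nothing here depends on it. The documents give no target or expected DLT rate, so every true rate below is an assumption.

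**What the data can show.** Exact (Clopper-Pearson) 95% intervals for the DLT rate. With no events the upper limit is 1 − 0.025^(1/n).
- 0 of 3: 0 to 1 − 0.025^(1/3) = 70.8%
- 0 of 6: 0 to 1 − 0.025^(1/6) = 45.9%
- 1 of 6: 0.4% to 64.1%

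**Chance that a level passes once it is tried.** Let p be the true DLT rate and q = 1 − p.
- On three patients: q³
- On 1 of 6 (one DLT in the first three, none in the next three): 3pq² × q³
- Now: the sum of these two
- With at most 1 of 6 required: q⁶ + 6pq⁵
- Share of current passes resting on three patients: q³ ÷ sum = 1/(1 + 3pq²)

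| p | 0 of 3 | 1 of 6 | passes now | six required | share on three |
|---|---|---|---|---|---|
| 10% | 0.729 | 0.177 | 0.906 | 0.886 | 0.805 |
| 20% | 0.512 | 0.197 | 0.709 | 0.655 | 0.723 |
| 33% | 0.301 | 0.134 | 0.434 | 0.358 | 0.692 |
| 40% | 0.216 | 0.093 | 0.309 | 0.233 | 0.698 |
| 50% | 0.125 | 0.047 | 0.172 | 0.109 | 0.727 |

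**Whole escalation, assumed rates 10%, 20% and 33% at Cohorts 1 to 3.** This takes the previous level as the MTD whenever a cohort fails, and leaves out any separate or intermediate cohort.
- Cohort 1 named: 0.906 × (1 − 0.709) = 0.264
- Cohort 2 named: 0.906 × 0.709 × (1 − 0.434) = 0.363
- Cohort 3 named: 0.906 × 0.709 × 0.434 = 0.279
- No level named: 1 − 0.906 = 0.094
- Named on three patients: 0.264 × 0.805 + 0.363 × 0.723 + 0.279 × 0.692 = 0.668, and 0.668/0.906 = 74% of named levels
- Cohort 3 (33%) named if six are required: 0.906 × 0.709 × 0.358 = 0.230, against 0.279 now

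**How often the quoted rule acts (same rates).** The chance of two or more DLTs in the first three is 0.104 at p = 20% and 0.255 at 33%. Cohort 2: 0.906 × 0.104 = 0.094. Cohort 3: 0.906 × 0.709 × 0.255 = 0.164. Together this is 26% of trials. The previous level then has only three patients in (0.094 × 0.805 + 0.164 × 0.723)/0.258 = 75% of them.

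**The case against.** The strongest reply is that the rule is deliberate and consistent. Protocol 3.2.1.1 and 7.6.4 and SAP 5.1 agree, and no document requires six patients at the MTD. That stands: this is a design choice, not a contradiction.

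The plan also has softer protections:
- Table 1 footnotes 1 and 2 have a reduced dose evaluated in a separate cohort. Reducing both drugs from Cohort 3 by the footnotes' examples gives the Cohort 2 dose, so patients could be added there. Under the assumed 10/20/33% rates, 0.164 of the 0.258 (63%) uses of the quoted rule fall at Cohort 3.
- The SRC may de-escalate, explore intermediate levels, and choose an optimal dose at or below the MTD. It must also approve expansion.
- Accrual is suspended after one death attributed to study drug (3.6.2), doses are modified for toxicity (7.7), and the Medical Monitor reviews adverse events regularly (12.3).

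These reduce the risk, and the footnote path means that the whole-escalation figures are approximate. None of them sets a six-patient minimum or a toxicity limit.

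A reader might infer that the reported MTD would be unsupported by its DLT data. The documents do not bear that out: 0 of 3 meets the plan's own definition, and the remedy also accepts 1 of 6, whose interval (0.4% to 64%) still includes 50%. A reader might also infer that the 2-of-first-3 rule removes the de-escalation option, since it lacks the clause found in the 2-of-6 rule. It does not: the opening paragraph of 3.2.1.1 gives the SRC that discretion generally.

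**Conclusion.** The point holds as a cheap improvement to patient safety, not as an error. The plan permits the expansion dose to be fixed on 0 of 3 DLTs, and under the assumed rates of 10/20/33% this would be the basis for about three in four named levels.

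The gain from requiring six is moderate. At 10/20/33% the level with a 33% DLT rate is named in 23% rather than 28% of trials. The larger per-level differences (43% to 36% at 33%; 31% to 23% at 40%) apply only once a level has been reached. The price is some extra rejection of tolerable doses: 71% to 66% at a 20% rate, and 91% to 89% at 10%. The interval for a clean result narrows from 0–71% to 0–46%.

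The reading of the text needs no assumption. The probabilities rest on assumed DLT rates, independent patients, and the written rules applied without SRC intervention.

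**What to change.** In Protocol 3.2.1.1 and 7.6.4, the synopsis and SAP 5.1, state that before expansion opens, the level chosen as MTD or optimal must have six DLT-evaluable patients with at most one DLT.

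If it has only 0 of 3, add three patients to that escalation cohort on the escalation Cycle 1 schedule: Tenalisib from Day 3, with PK sampling. If two or more of the six have a DLT, the SRC de-escalates.

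If the first three expansion patients are used instead:
- hold further enrolment until their 28-day window ends;
- note that they start Tenalisib on Day 1 and have no PK sampling, so the six would not share one Cycle 1 regimen;
- amend SAP 10.6.2 so that their DLTs are reported.

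The cost is at most three more patients and one 28-day window at the chosen level, or the enrolment hold alone, plus a few sentences of text. The preferred route stays within 3 to 6 per cohort and the maximum of 18 for three levels. The slightly higher chance of rejecting a tolerable dose is the remaining price.
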